## 5. Study Design

### 5.1. Summary of Study Design

Study I1F-JE-RHCV is a multicenter, open-label, post marketing clinical trial to evaluate the efficacy and safety of ixekizumab Q2W beyond Week 12 until Week 20 in patients with GPP and EP.

The study consists of 3 periods:

- **Period 1:** Screening Period (Visit 1) lasting from 7 to 30 days prior to Period 2 (baseline; Week 0; Visit 2)

Study investigator(s) will review patient history and screening test results to determine if the patient meets all inclusion and none of the exclusion criteria to qualify for participation in the study.

- **Period 2:** Induction Dosing Period from Week 0 (Visit 2) to Week 12 (Visit 6)

All eligible patients will be administered 160 mg ixekizumab as 2 SC injections at Week 0 (baseline; Visit 2) followed by 80 mg as 1 injection at Week 2, 4, 6, 8 and 10.

- **Period 3:** Maintenance Dosing Period from Week 12 to Week 20

Responders (GIS = 1 at Week 12) will complete the study.

Inadequate responders (GIS  $\geq 2$  at Week 12 and based on investigators' discretion) will continue to use ixekizumab 80 mg Q2W during Period 3. If patients show a therapeutic response (GIS = 1) with 80 mg Q2W after Week 12, the patient will complete the study. Patients who complete the study before Week 20 will have an early termination visit (ETV) instead of the original scheduled visit.

Figure RHCV.5.1 illustrates the study design.

[figure not shown]

Figure RHCV.5.1. Illustration of study design for Clinical Protocol I1F-JE-RHCV.

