## 6. A Priori Statistical Methods

### 6.1. General Considerations

Statistical analysis of this study will be the responsibility of Eli Lilly Japan.

Efficacy, health outcomes and safety analyses for Period 2 will be conducted on the largest analysis set (Full Analysis Set [FAS]), defined as the set of patients with GPP and EP separately who receive at least 1 dose of study treatment in Period 2 (FAS Population). Efficacy, health outcomes and safety analyses for Combined Periods 2 and 3 will be conducted based on patients with GPP and EP separately who receive at least 1 dose of study treatment in Period 3 (Maintenance Dosing Period Population) although the protocol stated that these analyses will be conducted only for Period 3 on the Maintenance Dosing Period Population.

Baseline for efficacy, health outcomes, and safety analyses in Period 2 and Combined Periods 2 and 3 is defined as the last available value before the first dose in Period 2; in most cases, it will be the value recorded at Week 0 (Visit 2).

Change from baseline will be calculated as the value at the visit of interest minus the baseline value. If all baseline values are missing for a particular variable, then the change from baseline and the percent improvement from baseline will not be calculated.

In the analysis of adverse events for Period 2 and Combined Periods 2 and 3, all pre-existing conditions recorded at Visit 1 and any on-study adverse events recorded prior to the first dose in Period 2 will be used as baseline events.

As this is a single arm study with very small sample size, no statistical inference will be performed.

Continuous data will be summarized in terms of the mean, standard deviation (SD), minimum, maximum, median, and number of observations. The minimum and maximum will be reported to the same number of decimal places as the raw data recorded in the database. The mean and median will be reported to 1 more decimal place than the raw data recorded in the database. The SD will be reported to 2 more decimal places than the raw data recorded in the database. In general, the maximum number of decimal places reported shall be 4 for any summary statistics. Categorical data will be summarized as frequency counts.

The statistical analyses will be performed using SAS® Version 9.4 or higher.

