### 6.13.2. Adverse Events

Adverse events will be classified based upon the latest version of the MedDRA. Adverse events will be recorded at every study visit. Any condition starting on or after the date of informed consent will be considered an AE. Any preexisting condition which worsens in severity on or after the date of informed consent will be considered and recorded as an AE on the *Adverse Events (AE)* eCRF page from the date of worsening onwards.

A treatment-emergent adverse event (TEAE) is defined as an event that first occurred or worsened in severity after baseline and on or prior to the date of the last visit within the defined treatment period. Both the date/time of the event and the date/time of the dose (that is, injection) are considered when determining TEAEs. The TEAEs will be assigned to the study period to which it's considered treatment-emergent:

- The MedDRA lowest level term (LLT) will be used when classifying AEs as treatment-emergent.
- The maximum severity recorded for each LLT prior to the first dose date/time in the treatment period will be used as the pre-treatment severity for that LLT. If an event during the baseline period has missing severity, and the event persists during the treatment period, then it will be considered as treatment-emergent, regardless of the postbaseline level of severity. Adverse events with a missing severity during the treatment period will be considered treatment-emergent.
- Adverse events with a particular LLT will be classified as treatment-emergent if they first start on or after the first dose date/time in the treatment period (i.e., a patient has no preexisting conditions with that LLT), or if the severity is greater than the pre-treatment severity for that LLT. If a partial AE start date/time is present, the date/time will be compared as far as possible to the treatment start date/time in order to determine whether the event is treatment-emergent or not. If there is any doubt, the event will be flagged as treatment-emergent.

Overall AEs and TEAEs will be summarized for the following study periods and analysis populations:

- Period 2 (Analysis population: FAS Population)
- Combined Periods 2 and 3 (Analysis population: Maintenance Dosing Period Population).

The following summaries will be provided for Period 2 and for Combined Periods 2 and 3 (Analysis population: FAS Population for Period 2, Maintenance Dosing Period Population for Combined Periods 2 and 3):

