- An overall summary of AEs including the number of patients who experienced TEAE, TEAE by maximum severity, death, SAE, TEAE possibly related to study treatment, discontinuation from the treatment due to an AE (including death), and treatment-emergent adverse events of special interest (AESIs)
- TEAE by maximum severity, system organ class (SOC) and preferred term (PT).

In general, events will be ordered by decreasing frequency in the total patient group (i.e., combined GPP and EP) within SOC and PT for sorting.

A by-patient listing of all AEs will be provided (Analysis population: FAS Population).

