### **6.16. Protocol Deviations**

Protocol deviations will be identified throughout the study. Important protocol deviations are defined as those violations from the protocol likely to have a significant impact on the completeness, accuracy, and/or reliability of the study data or that may significantly affect a subject's rights, safety, or well-being.

Important protocol deviations are identified in the TIMP. Refer to the latest version of TIMP.

The number of patients having important protocol deviations will be summarized within category and subcategory of deviations for Combined Periods 2 and 3 in patients with GPP and EP separately and total (Analysis population: FAS Population).

A by-patient listing of important protocol deviations will be provided (Analysis population: FAS Population).

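### No adverse event table in SAP 6.13 covers Weeks 0-20 for all treated patients; the combined-period summaries leave out anyone not dosed in Period 3

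*SAP*

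**What the plan says.** SAP 6.13.2 names two period-and-population pairs for the AE summaries: "Period 2 (Analysis population: FAS Population" and "Combined Periods 2 and 3 (Analysis population: Maintenance Dosing Period Population". SAP 6.13 says the same, and the summary column for each AE of special interest (AESI) in Table RHCV.6.3 lists the same two periods.

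SAP 6.1 defines the Maintenance Dosing Period Population as patients "who receive at least 1 dose of study treatment in Period 3 (Maintenance Dosing Period Population". SAP 6.9 puts the first Period 3 injection at Week 12. For the combined period, SAP 6.1 sets the baseline before the first Period 2 dose, so events are counted from Week 0.

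The overall table has rows for treatment-emergent AEs (TEAEs), maximum severity, death, serious AEs and related TEAEs, and also for "discontinuation from the treatment due to an AE (including death), and treatment-emergent adverse events of special interest (AESIs". A second table gives TEAEs by severity, system organ class (SOC) and preferred term (PT).

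Patients can be outside the Maintenance Dosing Period Population for ordinary reasons. SAP 5.1 says: "Responders (GIS = 1 at Week 12) will complete the study".

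Three other places matter:
- By-patient data: "A by-patient listing of all AEs will be provided (Analysis population: FAS Population". SAP 6.13.3 and 6.13.3.1 add FAS listings of deaths, serious AEs, AE discontinuations and each special safety topic.
- Protocol deviations (SAP 6.16) are summarised "for Combined Periods 2 and 3 in patients with GPP and EP separately and total (Analysis population: FAS Population".
- The related-TEAE table in SAP 6.18 and the registry AE summary in SAP 6.19 state neither a population nor a period.

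**The concern.** The combined table starts its count at Week 0 but selects its patients by something that happens at Week 12 or later. A patient who dies or stops for an AE during induction is removed from both numerator and denominator.

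The protocol did not have this mismatch. Its Section 10.3.4 planned Period 2 on the FAS and Period 3 alone on the Maintenance Dosing Period Population, and its Section 10.3.1 set the Period 3 safety baseline at about Week 12. Entry to the population and start of counting therefore coincided. The SAP moved the start of counting back to Week 0 and kept the entry condition. SAP 6.1 records the change openly but gives no reason and no caution.

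At stake is how the only 20-week AE table is read. Protocol 3.3 reports no serious AEs and no AE discontinuations in EP and GPP patients on the initially approved regimen, so a single such event here would be noticed. The combined table could show none after one had occurred in induction. For the other rows, a reader who wants the number of treated patients affected over the trial will not find it in the SAP 6.13 tables.

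**Working it through.** **Planned denominator.** Protocol 10.1 and SAP 5.2 plan 12 patients so that at least 5 with EP and 5 with GPP continue. No formula is given. In the earlier study cited there, 4 of 5 GPP and 7 of 8 EP patients had GIS = 2 at Week 12, which is 11 of 13. Then 10 / (11/13) = 11.8, rounded up to 12, which agrees with the plan. By disease, 5/0.80 = 6.25 and 5/0.875 = 5.71, so 7 + 6 = 13, one more than planned.

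**How many treated patients the combined table leaves out.**
- With the earlier rates and an assumed split of 6 + 6, expected continuers are 6 × 0.80 + 6 × 0.875 = 4.80 + 5.25 = 10.05.
- If 10 continue, 12 − 10 = 2 are left out (2/12 = 17%).
- SAP 5.2 also assumes about 5 continuers at most, without saying whether per disease or in total. If in total, 12 − 5 = 7 are left out (7/12 = 58%).

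**What can be recovered from the two tables.** For a given row, let
- a = patients with the event in the Period 2 FAS table, a = a_in + a_out, where a_in later had a Period 3 dose and a_out did not;
- b = patients with the event in the combined table;
- W = treated patients with the event over the whole trial.

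Patients with no Period 3 dose have all their treatment in Period 2, so W = a_out + b. The tables show a and b, but not a_out.

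*Death and AE discontinuation.* Nobody with either event before the first Period 3 dose enters the Maintenance Dosing Period Population. So a_in = 0, a_out = a and W = a + b. Illustration with assumed counts: 2 of 12 stop for an AE in Period 2, 10 continue, and 1 of these stops in Period 3. The tables show 2/12 and 1/10, and W = 2 + 1 = 3 of 12 (25%). This assumes that a discontinuation is assigned to the period in which treatment stopped.

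*All other rows.* A patient with a TEAE in Period 2 who continues is counted in both a and b. Then a_in is not zero in general, and W is known only within limits:
- a_out cannot exceed the number left out, nor a;
- a_in = a − a_out cannot exceed b.

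With assumed counts:

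| Continuers | a | b | Possible a_out | W = a_out + b |
|---|---|---|---|---|
| 10 | 6 | 7 | 0 to 2 | 7 to 9 of 12 |
| 5 | 6 | 4 | 2 to 6 | 6 to 10 of 12 |

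The FAS listings would settle W patient by patient.

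**The case against.** The strongest case on the other side is that this is presentation, not lost data. Every induction event in every treated patient is in the Period 2 FAS table, and the FAS listings cover all AEs, deaths, serious AEs, AE discontinuations and special safety topics. With about 12 patients, any total can be counted by hand. SAP 6.7 also tabulates treatment discontinuation by reason for each period. The study objective concerns dosing beyond Week 12, and the combined table describes exactly those patients, with the population named each time. All of this stands, and it keeps the point small.

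Three stronger readings are tempting, and the documents do not support them:
- A reader might infer that the whole-trial number of AE discontinuations or deaths cannot be obtained. It can: those two rows come from different patients and add.
- A reader might infer that no table at all gives whole-trial AE counts. That is unproven, because SAP 6.18 and 6.19 do not state their populations. The SAP shows only that no table in 6.13 does.
- A reader might call this immortal-time bias, with 12 of 20 weeks (60%) unable to contain a terminal event. The SAP plans no person-time rate, comparison or inference, so that share affects no planned result.

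Two further objections have some force. A FAS table over Weeks 0-20 mixes Week 12 responders with patients treated longer, which can lower crude frequencies. And SAP 6.16 concerns protocol deviations, which depend less on exposure. The first is met by showing exposure alongside. The second weakens 6.16 as a precedent, but it still shows that the combination is already in use. What remains unanswered is the overlap in the non-terminal rows.

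**Conclusion.** The point holds as a gap in tabulation. The combined AE and AESI summaries cannot contain a Week 0-12 death or AE discontinuation, and the SAP 6.13 tables do not give the number of treated patients with any TEAE, serious AE or AESI, or by severity or SOC/PT, over the whole trial. For those rows the total is uncertain by 2 patients (7 to 9) or 4 patients (6 to 10) of 12 in the illustrations.

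The omission is 2 of 12 treated patients if 10 continue and 7 of 12 if 5 do. The first follows from the enrolment target, and the second from one reading of an ambiguous sentence in SAP 5.2. The event counts are assumed; if no induction event ends treatment, the effect on the death and AE-discontinuation rows is zero. In a small descriptive study with full listings this is a worthwhile, inexpensive improvement, not a threat to the conclusions.

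**What to change.** - In SAP 6.13.2 and the AESI overall summaries in Table RHCV.6.3, add a FAS version of the Combined Periods 2 and 3 summary: all treated patients, first dose to end of participation, by disease and total.
- Put FAS exposure for the same period beside it, because Week 12 responders contribute only about 12 weeks. SAP 6.13.1 currently summarises combined-period exposure only on the Maintenance Dosing Period Population.
- Keep the Maintenance Dosing Period Population version, with a footnote that deaths and AE discontinuations before the first Period 3 dose are excluded by definition.
- State the population and period for the summaries in SAP 6.18 and 6.19.

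The cost is a rerun of summaries already planned on a population already defined, one footnote and two sentences of text. No new data are needed. The small downside is unequal follow-up in the FAS version, which the exposure summary makes visible.

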### **6.13.3. Deaths, Other Serious Adverse Events, and Other Notable Adverse Events**

By-patient listings of deaths, SAEs, and AEs leading to treatment discontinuation will be provided (Analysis population: FAS Population).

All deaths will be included, regardless of the investigator's or the sponsor's judgment about causality, including:

- any deaths occurring during participation in the study in the database for which data are being presented
- any deaths occurring after a patient leaves (is discontinued from or completed) the study in the database for which data are being presented if the death is the result of a process initiated during the study, regardless of when it actually occurred.

An SAE is any AE that results in one of the following outcomes: death, life-threatening, initial or prolonged hospitalization, disability or permanent damage, congenital anomaly or birth defect, or any other serious/important medical events.

#### **6.13.3.1. Special Safety Topics including Adverse Events of Special Interest**

Safety information on special topics including AESIs will be provided.

[Table RHCV.6.3](#) provides the definitions and derivations of special safety topics including AESIs.

Potential AESIs will be identified by a standardized MedDRA query (SMQ) or a Lilly-defined MedDRA PT listing. Preferred terms within an SMQ will be classified as broad and narrow. In the Lilly-defined MedDRA PT listings, Lilly has provided the broad and narrow classification. The Lilly-defined broad terms are for a more sensitive search of potential events of interest and the Lilly-defined narrow terms are for a more specific search.

In the event that the listing of terms or analysis changes for a special safety topic, it will be documented in the Program Safety Analysis Plan (PSAP) which will supersede this document; it will not warrant an amendment to the individual study SAP.

By-patient listings of each special safety topic will be provided (Analysis population: FAS Population).

Table RHCV.6.3. Definitions and Derivations of Special Safety Topics including Adverse Events of Special Interest

Special Safety Topic	Definition / Derivation	Summary / Listing
Hepatic	
Hepatic AE will include events that are potentially drug-related hepatic disorders by using the MedDRA PTs contained in any of the following SMQ or sub-SMQ as defined in MedDRA:
 
 
• Broad and narrow terms in the Liver related investigations, signs and symptoms (20000008)
 
• Broad and narrow terms in the Cholestasis and jaundice of hepatic origin (20000009)
 
• Broad and narrow terms in the Hepatitis, non-infectious (20000010)
 
• Broad and narrow terms in the Hepatic failure, fibrosis and cirrhosis and other liver damage (20000013)
 
• Narrow terms in the Liver-related coagulation and bleeding disturbances (20000015).
 
	
Overall summary:
 
 
● Period 2
 
● Combined Periods 2 and 3
 
 
Listing: TEAE (included in the same listing with cytopenia, depression and interstitial lung disease AESIs)

Cytopenias	
Cytopenias are defined using the PTs from the following 2 sub-SMQs of the Haematopoietic cytopenias SMQ (20000027) as specified in MedDRA:
 
 
• Broad and narrow terms in the Haematopoietic leukopenia (20000030)
 
• Broad and narrow terms in the Haematopoietic thrombocytopenia (20000031).
 
	
Overall summary:
 
 
● Period 2
 
● Combined Periods 2 and 3
 
 
Listing: TEAE (included in the same listing with hepatic, depression and interstitial lung disease AESIs)

Infections	
Infections are events including all infections (defined using all the MedDRA PTs from the Infections and infestations SOC), serious infections, potential opportunistic infections, and infections resulting in anti-infective medication administration (i.e. antibacterial, antivirals, antifungals, antiparasitic treatments).
 
Listing of patients experiencing a TEAE of infections will include the following additional information: types of infection, potential opportunistic infections (OIs) (Yes/No), anti-infective medications use (if treated) with medication start/end dates, indication for use, and route; minimum postbaseline value within each treatment period for leukocytes, platelets, lymphocytes, and absolute neutrophils. Anti-infective medications are defined in Appendix 5 of the PSAP Version 8. The list of MedDRA terms used to identify infections that are predefined as potential OIs are found in Appendix 10 of the PSAP Version 8.
	
Overall summary:
 
 
● Period 2
 
● Combined Periods 2 and 3
 
 
Listing: TEAE (including information collected on Infection eCRF page)

Allergic Reactions/Hypersensitivities	
Allergic reactions/hypersensitivity events will be categorized as either anaphylaxis or non-anaphylaxis events (these will refer to events that are not localized to the site of injection) and summarized separately.
 
Allergic Reactions/Hypersensitivity Events, Anaphylaxis: Anaphylaxis has been broadly defined as “a serious allergic reaction that is rapid in onset and may cause death” (Sampson et al. 2006).
	
Overall summary:
 
 
● Period 2
 
● Combined Periods 2 and 3
 

Special Safety Topic	Definition / Derivation	Summary / Listing
	
Identification of cases of potential anaphylaxis from the clinical trial data involves two criteria:
 
 
1) designed to specifically identify cases (following Criterion 1) based on narrow terms from the MedDRA SMQ for anaphylactic reaction (20000021). Criterion 1 for anaphylaxis is defined by the presence of a TEAE based on the following MedDRA PTs from the anaphylactic reaction SMQ: 
 
• Anaphylactic reaction
 
• Anaphylactic shock
 
• Anaphylactoid reaction
 
• Anaphylactoid shock
 
• Kounis Syndrome
 
• Type 1 hypersensitivity.
 
 
 
2) to identify possible cases, following Criterion 2 as defined by Sampson et al. (2006). Criterion 2 for anaphylaxis requires having TEAEs from two or more of four categories of AEs as described by Sampson et al. (2006). Occurrence of these events should be nearly coincident based on recording of events on the eCRF. All qualifying event must be within 1 day of study drug injection.
 
 
The 4 categories to be considered in Criterion 2 are:
 
 
• Category A: Involvement of the skin-mucosal tissue
 
• Category B: Respiratory compromise
 
• Category C: Reduced blood pressure or associated symptoms
 
• Category D: Persistent gastrointestinal symptoms.
 
 
The specific MedDRA PTs covered by each of these Criterion 2 categories are shown in Appendix 6 of the PSAP Version 8.
 
Criterion 2 anaphylactic TEAEs will be defined by the specific combination of categories as follows:
 
 
• AB: events based on meeting Category A and Category B (but no other category)
 
• AC: events based on meeting Category A and Category C (but no other category)
 
• AD: events based on meeting Category A and Category D (but no other category)
 
• BC: events based on meeting Category B and Category C (but no other category)
 
• BD: events based on meeting Category B and Category D (but no other category)
 
• CD: events based on meeting Category C and Category D (but no other category)
 
• ABC: events based on meeting Category A, Category B and Category C (but no other category)
 
• ABD: events based on meeting Category A, Category B and Category D (but no other category)
 
• ACD: events based on meeting Category A, Category C and Category D (but no other category)
 
	

Special Safety Topic	Definition / Derivation	Summary / Listing
	
category)
 
 
• BCD: events based on meeting Category B, Category C and Category D (but no other category)
 
• ABCD: events based on meeting each of the 4 Criterion 2 categories.
 
 
Overall summaries of treatment-emergent anaphylactic AEs will be provided for patients who meet either criteria.
 
Allergic Reactions/Hypersensitivity Events, Non-Anaphylaxis: TEAEs of allergic reaction/hypersensitivity categorized as non-anaphylaxis events are defined by the narrow terms within Hypersensitivity SMQ (20000214) excluding the PTs noted in Appendix 7 of the PSAP Version 8 and excluding the anaphylactic events as defined above.
 
A by-patient listing will be provided for all patients experiencing TEAE of allergic reactions/hypersensitivities at any time, including status/criterion of anaphylaxis or non-anaphylaxis, and the associated information collected on Hypersensitivity, Anaphylactic, and Infusion Related Reactions eCRF page.
	
Injection Site Reactions	
Injection site reaction is defined using the PTs from the MedDRA HLT of Injection site reactions as specified by MedDRA excluding the following 10 PTs:
 
 
1) Embolia cutis medicamentosa
 
2) Injection site joint discomfort
 
3) Injection site joint effusion
 
4) Injection site joint erythema
 
5) Injection site joint infection
 
6) Injection site joint inflammation
 
7) Injection site joint movement impairment
 
8) Injection site joint pain
 
9) Injection site joint swelling
 
10) Injection site joint warmth.
 
	
Overall summary:
 
 
● Period 2
 
● Combined Periods 2 and 3
 
 
Listing:
 
TEAE (including information collected on Injection Site Reaction eCRF page)

Cerebro-cardiovascular Events	
Cerebro-cardiovascular events will be externally adjudicated by the Clinical Events Committee (CEC) made up of a chairman, 2 cardiologists, and a neurologist. The CEC will adjudicate investigator-reported events selected for adjudication and render an assessment as to whether the event represents a confirmed event (meeting the event definition with all necessary documentation), a non-event (does not meet the event definition and likely represents an alternative or nonevent diagnosis), or lacks sufficient documentation for confirmation of an event. Confirmed cerebro-cardiovascular events by CEC will be
	
Overall summary:
 
 
● Period 2
 
● Combined Periods 2 and 3
 
 
Listing:
 
TEAE

Special Safety Topic	Definition / Derivation	Summary / Listing
	
summarized overall. All events which qualify for CEC adjudication will be listed. The categories and subcategories of adjudicated events used for the listing will include the following:
 
 
• Cardiovascular                             
 
○ Death (Cardiovascular)
 
○ Cardiac Ischemic Event: Myocardial Infarction and Hospitalization for Unstable Angina
 
○ Serious Arrhythmia
 
○ Hospitalization for Heart Failure
 
○ Hospitalization for Hypertension
 
○ Resuscitated Sudden Death
 
○ Cardiogenic Shock
 
○ Coronary Revascularization.
 
 
 
• Neurologic                             
 
○ Cerebrovascular Event: Transient Ischemic Attack or Stroke (Hemorrhagic, Ischemic and Undetermined).
 
 
 
• Peripheral Vascular Events                             
 
○ Peripheral Arterial Event
 
○ Peripheral Revascularization.
 
 
 
 
Listing of patients experiencing a cerebro-cardiovascular TEAE will include the following additional information: CEC assessment (confirmed event, no event, or insufficient documentation for event determination), categories/subcategories of adjudicated events, subtypes of stroke (Hemorrhagic Stroke, Ischemic Stroke, and Undetermined Stroke Type), major adverse cerebro-cardiovascular events (MACE defined below; Yes/No), and subcategories of MACE (Vascular Death, Non-fatal myocardial infarction, and Non-fatal stroke).
	
Major Adverse Cerebro-Cardiovascular Events (MACE)	
MACE (requiring adjudication as defined above) is defined as:
 
 
• Vascular Death (including cardiovascular and cerebro-vascular causes excluding hemorrhagic deaths outside of the central nervous system)
 
• Non-fatal myocardial infarction
 
• Non-fatal stroke (subtypes: hemorrhagic stroke, ischemic stroke, undetermined stroke type).
 
 
Where,
 
 
• Vascular death should be captured as an Event on Adjudication - Death eCRF page with Adjudication Death Type = ‘Cardiovascular’.
 
• Non-fatal myocardial infarction should be captured as an Event on Adjudication - Cardiac Ischemic Event eCRF page with Type of Ischemic Event = “Myocardial Infarction” and the Event
 
	
Listing: TEAE (included in the same listing with cerebro-cardiovascular events)

Special Safety Topic	Definition / Derivation	Summary / Listing
	
is NOT on Adjudication - Death eCRF page.
 
 
Non-fatal strokes (ischemic, hemorrhagic) should be captured as an Event on Adjudication - Cerebrovascular Event eCRF page with Stroke Cerebrovascular Event Subtype in one of the following categories: hemorrhagic stroke, ischemic stroke, undetermined stroke type, and the Event is NOT on Adjudication - Death eCRF page.
 
	
Malignancies	
Malignancy is defined using PTs from the Malignant or unspecified tumors SMQ as specified in MedDRA (SMQ: 20000091, which includes the sub-SMQs:
 
 
20000194 [Malignant tumours], including sub-SMQs of 20000227 [Haematological malignant tumours] and 20000228 [Non-haematological malignant tumours]
 
20000195 [Tumours of unspecified malignancy], including sub-SMQs of 20000229 [Haematological tumours of unspecified malignancy] and 20000230 [Non-haematological tumours of unspecified malignancy].
 
 
Events will be categorized as follows:
 
 
Nonmelanoma Skin Cancer (NMSC) 
 
Basal Cell Carcinoma, PTs include: 
 
Basal cell carcinoma
 
Basosquamous carcinoma
 
Basosquamous carcinoma of skin.
 
 
 
Squamous Cell Carcinoma, PTs include: 
 
Squamous cell carcinoma of skin
 
Bowen’s disease
 
Lip squamous cell carcinoma
 
Skin squamous cell carcinoma metastatic
 
Keratoacanthoma.
 
 
 
 
 
Malignancies excluding NMSC: all PTs in the Malignant or unspecified tumors SMQ excluding the 8 defined NMSC PTs.
 
	
Overall summary:
 
 
Period 2
 
Combined Periods 2 and 3
 
 
Listing: TEAE

Depressions	
Depression is defined using the PTs from the Depression and suicide/self-injury SMQ as specified in MedDRA (SMQ: 20000035, which includes the sub-SMQs: 20000037 [Suicide/self-injury] and 20000167 [Depression (excl suicide and self-injury)]).
	
Overall summary:
 
 
Period 2
 
Combined Periods 2 and 3
 
 
Listing: TEAE (included in the same listing with hepatic, cytopenia and

Special Safety Topic	Definition / Derivation	Summary / Listing
Inflammatory Bowel Disease (IBD)	
IBD will be identified using the following subcategory and MedDRA PTs. The narrow terms are considered IBD and summarized overall. IBD events will also be externally adjudicated by the CEC with expertise in IBD.
 
IBD (Narrow terms)
 
 
• Inflammatory Bowel Disease: Inflammatory bowel disease
 
• Crohn’s Disease: Crohn’s disease
 
• Ulcerative Colitis: Acute haemorrhagic ulcerative colitis; Colitis ulcerative; Proctitis ulcerative.
 
 
Non-Specific Terms (Events That Can Occur with IBD (Broad Terms)): The PTs in this category are listed in Appendix 11 of the PSAP Version 8.
	
interstitial lung disease AESIs)
 
Overall summary:
 
 
● Period 2
 
● Combined Periods 2 and 3
 
 
Listing: TEAE (including adjudicated results)

Interstitial Lung Disease (ILD)	
ILD is defined using the following terms:
 
 
• Broad and narrow terms in the Interstitial lung disease SMQ (20000042)
 
• Additional 6 PTs from Eosinophilic pneumonia SMQ (20000157):                             
 
○ Angiolymphoid hyperplasia with eosinophilia (Narrow)
 
○ Eosinophilic bronchitis (Narrow)
 
○ Hypereosinophilic syndrome (Narrow)
 
○ Loeffler’s syndrome (Narrow)
 
○ Pulmonary eosinophilia (Narrow)
 
○ Pulmonary vasculitis (Narrow).
 
 
 
	
Overall summary:
 
 
● Period 2
 
● Combined Periods 2 and 3
 
 
Listing: TEAE (included in the same listing with hepatic, cytopenia and depression AESIs)

Abbreviations: AE = adverse event; AESI = adverse event of special interest; eCRF = electronic case report form; HLT = high-level term; OI =opportunistic infection; PT = preferred term; SAE = serious adverse event; TEAE = treatment emergent adverse event.

